#### Supportive estimand 3:

**Population:** Adult moderate to severe atopic dermatitis patients as defined by the study inclusion and exclusion criteria who were randomized to treatment, and not mis-randomized in the IRT. This implies that analyses will be based on the full analysis set.

**Endpoint:** IGA response at week 16, where IGA response is defined as an IGA score of 0 or 1 with at least a 2 point improvement compared to baseline and no use of confounding therapy before the assessment time point.

**Treatment of interest:** the randomized treatment (ZPL389 or placebo) plus medications as allowed by the protocol but with no further treatment for patients who discontinue study treatment due an AE or lack of efficacy.

#### Handling of remaining intercurrent events:

• Treatment discontinuations for any reason: consider as non-responder at week 16

Novartis	For business use only	Page 22
SAP		CZPL389A2203

The summary measure: difference in response rates between ZPL389 and placebo.

This estimand is intended to assess the "worst case" situation where any discontinuation of study treatment is considered to represent lack of efficacy regardless of the reason entered on the CRF for the discontinuation. Given that a larger than expected proportion of patients gave "subject decision" as the reason for discontinuation this estimand will also help to address the question of whether ZPL389 is effective under the worst case assumption about what response would have been if patients had remained on treatment.

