Investigational drug	The drug whose properties are being tested in the study; this definition is consistent with US CFR 21 Section 312.3 and is synonymous with "investigational new drug" or "investigational medicinal product."
IGA Response	IGA response is defined as achieving an IGA score of 0 (clear) or 1 (almost clear) and at least 2 points reduction from Baseline and no use of confounding therapy as adjudicated up to the assessment time point.
Medication pack number	A unique identifier on the label of each investigational drug package
Patient	A person with the condition of interest being studied
Period	Interval of time in the planned conduct of a study. A period is associated with a purpose (e.g. screening, treatment, follow-up), which applies across all arms of a study.
Personal data	Subject information collected by the Investigator that is transferred to Novartis for the purpose of the clinical trial. This data includes subject identifier information, study information and biological samples.
Subject	A patient participating in this study
Subject number	A unique number assigned to each subject upon signing the informed consent
Randomization number	A unique identifier assigned to each randomized subject, corresponding to a specific treatment arm assignment
Source Data/Document	Source data refers to the initial record, document, or primary location from where data comes. The data source can be a database, a dataset, a spreadsheet or even hard-coded data, such as paper or eSource.
Study drug/ treatment	Any single drug or combination of drugs administered to the subject as part of the required study procedures; includes investigational drug (s), placebo/comparator active drug run-ins or background therapy
Study Treatment Discontinuation (TD)	When the subject permanently stops taking study treatment prior to the defined study treatment completion date
Variable	A measured value or assessed response that is determined in specific assessments and used in data analysis to evaluate the drug being tested in the study

Glossary of terms

Withdrawal of study	Withdrawal of consent from the study occurs only when a subject does not
consent (WoC)	want to participate in the study any longer, and does not allow any further
	collection of personal data

Amendment 3 (02 September 2019)

Amendment rationale

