5.6.5 Early study termination by the sponsor

The study can be terminated by Novartis at any time for any reason.

Reasons for early termination:

- Unexpected, significant or unacceptable safety risk to subjects enrolled in the study
- Decision based on recommendations from applicable board(s) after review of safety and efficacy data
- Discontinuation of study drug development

In taking the decision to terminate, Novartis will always consider subject welfare and safety. Should early termination be necessary, subjects must be seen as soon as possible and treated as a prematurely withdrawn subject. The investigator may be informed of additional procedures to be followed in order to ensure that adequate consideration is given to the protection of the subject's interests. If the study is terminated prematurely the investigator or treating physician must ensure appropriate ongoing care is provided to the patient. The investigator will be responsible for informing IRBs/IECs of the early termination of the trial.

6 Visit schedule and assessments

Table 6-1 lists all of the assessments/actions and indicates with an "X" or "S" at which visits they are performed.

Subjects must be seen for all visits on the designated day, or as close to it as possible. Missed or rescheduled visits should not lead to automatic discontinuation. Subjects who prematurely discontinue from the study should have at the time of discontinuation all of the assessments listed for the End of Treatment Week 16 visit, and a Follow-up Week 20 visit. All e-diaries and devices and study medication must be returned to the site at this visit. At this final visit, all dispensed investigational product should be reconciled and the adverse event and concomitant medications reconciled on the CRF.

Subjects should be reminded to be fasting for at least 3 hours before the visits and to bring their medication and their e-diaries. They should not eat at least until the last ECG is performed.

Novartis	
Amended Protocol Version 03 (clean)	

Period	Screening	Treatment					Follow-up (EOS/PSW)	Unplanned		
Visit Day	-28 to -1	1	15	29	43	57	85	113 ¹	141	-
Weeks	-4 to -1	0	2	4	6	8	12	16	20	0
Informed consent	Х									
Demography, AD medical history, Medical history/current medical conditions, Smoking history	х									
Inclusion / Exclusion criteria	Х	Х								
Randomization		Х								
Physical Examination	S	S	S	S	S	S	S	S	S	S

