# 1.1 Study design

The core study (A2203) was planned as a randomized, double blind, placebo controlled, parallel group, 5-arm study in at least 360 subjects with moderate to severe Atopic Dermatitis (AD). Unbalanced randomization ratio was used, intending to result in approximately 90 subjects randomized in each of the 30 mg/day and 50 mg/day dose arms as well as in the placebo arm, and 45 subjects in each of the 3 mg/day and 10 mg/day arms. The randomization was stratified by baseline severity of atopic dermatitis (IGA score moderate or severe) and by geographical region.

The possibility to perform an interim analysis (IA) in order to support decision making concerning the current clinical study or project was addeded to the protocol in V3. This interim analysis was performed in May 2020 on 187 patients who had completed week 16 or discontinued before this timepoint. Based on the results from this IA, it was decided to stop both the core and extension studies for reasons of lack of efficacy and thus the final number of patients, and follow-up time per patient is less than planned in the protocol.

The core study (A2203) consisted of a screening period of up to 4 weeks (depending on current medication use and associated washout period), and a 16-week double blinded treatment period. The primary endpoint was to be assessed at the end of the 16 week treatment period.

After the end of treatment visit, subjects were offered the possibility of ongoing treatment in the extension study (A2203E1), or of entering the 4 week treatment-free follow up period.

[figure not shown]

The extension study (A2203E1) was intended to be a randomized, double blind, parallel group, 2-arm study in up to approximately 202 to 230 subjects. This number assumed a discontinuation rate of 15% to 25% in the core study (A2203)

In the extension study, subjects who had received ZPL389 30 mg o.d. or 50 mg o.d. doses in the core study, would continue to receive the same doses in a double-blinded fashion. Subjects who had received ZPL389 3 mg, 10 mg or placebo in the core study, would be randomized to receive ZPL389 30 mg o.d. or 50 mg o.d. in a 1:1 ratio. All subjects would receive concomitant or intermittent topical corticosteroids (TCS) and/or topical calcineurin inhibitors (TCI) along in a standardized regimen with ZPL389.

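### Supportive estimand 3 makes no exception for sponsor closure, so any core patient stopped by closure before Week 16 is scored as an IGA failure (minor, cheap to fix)

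*SAP*

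**What the plan says.** SAP 2.5.4 defines three supportive estimands that vary how treatment discontinuation is handled. The third uses the rule "Treatment discontinuations for any reason: consider as non-responder at week 16". Its explanation calls this a worst case in which "any discontinuation of study treatment is considered to represent lack of efficacy regardless of the reason entered on the CRF for the discontinuation". It then adds a second purpose: more patients than expected gave their own decision as the reason for stopping.

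The SAP's document history is dated 29 September 2020. Its introduction says that it reflects changes made after the decision to stop both studies. SAP 1.1 records that after the May 2020 interim analysis "it was decided to stop both the core and extension studies for reasons of lack of efficacy", and that the final number of patients is below plan and "follow-up time per patient is less than planned in the protocol".

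The other estimands treat the same event differently. The primary estimand (SAP 2.5.1) scores only stops for lack of efficacy or adverse event as failures. Data after any other stop become missing and are imputed (SAP 2.5.3). Supportive estimands 1 and 2 set data after every stop to missing. SAP 2.6.1 carries all three supportive estimands over to EASI50 and EASI75 response at Week 16, and SAP 2.6.5 carries them over to the analyses by visit.

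**The concern.** A worst-case analysis of dropout asks whether the conclusion survives if patients who left, for whatever stated reason, had in truth failed. That is a fair question about a patient who chose to stop. It has no bearing on a patient who was on treatment and was stopped because the sponsor ended the study: the cause is the calendar date of closure, not the state of the skin.

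If the two groups are pooled, a gap between supportive estimand 3 and the primary estimand has two possible sources, patient-driven dropout and administrative cut-off, and the tables would not tell them apart. Response rates from this analysis would also be too low in every arm that has closure stops, which matters if they are read beside rates from other trials. The SAP adapted other parts of the analysis to the early stop, but no intercurrent-event rule mentions closure.

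**Working it through.** **Step 1. Does the rule reach closure stops?** The Protocol glossary defines study treatment discontinuation as "When the subject permanently stops taking study treatment prior to the defined study treatment completion date", without regard to the reason. Protocol 5.6.5 says that at sponsor termination "subjects must be seen as soon as possible and treated as a prematurely withdrawn subject". Protocol 5.6.2 is narrower: it names only the subject and the investigator as those who can initiate a discontinuation. Supportive estimand 3 covers every reason and disregards the one on the CRF, so as worded it includes closure stops. If the narrower text was meant to govern, the SAP does not say so, and these patients would have no stated handling.

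**Step 2. Who can be affected?** Only core patients on treatment before Week 16 when closure took effect. Patients stopped in the extension had passed the core period. The interim analysis was "performed in May 2020 on 187 patients who had completed week 16 or discontinued before this timepoint", so the Week 16 status of those 187 was already settled. SAP section 3 says the final total is below the planned 360. Closure stops in the core study therefore number fewer than 360 − 187 = 173, or below 173/360 = 48% of all patients. This is a loose ceiling and not an estimate, because patients outside the 187 may have finished Week 16 or left for other reasons before closure. The actual count is not given.

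**Step 3. Planning inputs.** Protocol 9.8 assumes a 10% placebo response, a maximum effect of 20 points (so 30%), 360 patients split 90:45:45:90:90, one-sided alpha 2.5% and 90% power. A simulation of the MCP-Mod maximum-contrast test with the seven shapes in Protocol 9.4.2 gives a minimum power of 91.7% on the logit scale with variances under the alternative. Other variants (proportion scale, or pooled null variance) give 95.8% to 96.9%. The smallest total reaching 90% is 340 in the first case and 270 to 280 in the others. So the stated power is met, closely in one variant, but 360 is not reproduced as the minimum. This check does not bear on the closure rule. It only supplies the rates 10% and 30% as an illustration.

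**Step 4. Effect of the rule.** Let p be an arm's response rate without closure and f the share of the arm stopped by closure before Week 16. If those patients would otherwise have responded at rate p, scoring them as failures gives an expected rate of p(1 − f). With the same f in both arms, the difference is (p₁ − p₀)(1 − f). The values of f are assumptions.

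| f | placebo, 10% × (1 − f) | active, 30% × (1 − f) | difference | odds ratio |
|---|---|---|---|---|
| 0 | 10.0% | 30.0% | 20.0 points | 3.86 |
| 5% | 9.5% | 28.5% | 19.0 points | 3.80 |
| 10% | 9.0% | 27.0% | 18.0 points | 3.74 |
| 20% | 8.0% | 24.0% | 16.0 points | 3.63 |
| 40% | 6.0% | 18.0% | 12.0 points | 3.44 |

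The odds ratio is [p₁/(1 − p₁)] / [p₀/(1 − p₀)] at the shrunken rates. It moves much less than the difference, which is the SAP's summary measure.

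**Step 5. No true effect.** With p₁ = p₀ and equal f, the difference stays at zero and only the rates fall. With unequal f it becomes p₁(1 − f₁) − p₀(1 − f₀). For example, true rates of 10% in both arms, with f = 10% on placebo and 20% on active, give 8.0% − 9.0% = −1.0 point.

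**The case against.** The case for leaving the text alone has four parts.

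- **The rule is declared.** Scoring every stop as failure is the estimand's stated definition and its first purpose; the patients' own decision comes second. A reader might infer that the rule was written only for patient-driven stops and contradicts its own rationale. The text does not support that. What stands is narrower: the worst-case label does not make an administrative stop informative about response.
- **The rule predates the stop.** Protocol 9.4.4 already planned a sensitivity analysis counting discontinuation for any reason as non-response. An exception made after interim results is a further change. That is a real cost, and a reason to show both versions.
- **Closure stops before Week 16 are not documented.** A reader might infer from the early stop that core patients were in fact cut off mid-treatment. The documents do not say so. Shorter follow-up could come from the extension, which was planned to run to Week 116, and SAP 2.3.1 names only disposition in the extension as disrupted. Some core cut-offs are plausible under Protocol 5.6.5, but the number could be small.
- **Little depends on it.** The trial was stopped for lack of efficacy, this analysis is supportive, and three of the four IGA estimands already set such data to missing.

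A reader might also infer that the rule dilutes the treatment effect in this trial. SAP section 4 reports no treatment effect at the interim analysis. If the true difference is near zero, equal closure shares leave next to nothing to dilute.

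**Conclusion.** The gap in the wording is real and its consequence is small. As written, supportive estimand 3 counts any core patient stopped by closure before Week 16 as an IGA failure, and the same holds for EASI50 and EASI75.

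Its size cannot be computed, because the closure share is not in the documents. The factor 1 − f rests on two assumptions: closure is unrelated to response, and the share is equal across arms. The second is reasonable on average, since entry date should not depend on the randomised arm, but it can fail by chance. The 19, 18 and 16 points illustrate the planning scenario and do not predict this trial's result. If there is no true effect, the consequence is lower absolute rates plus whatever small difference unequal closure shares create.

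The primary estimand and supportive estimands 1 and 2 are not affected by this rule. The documents do not support calling the analysis invalid. The label is a cheap improvement, of minor severity.

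**What to change.** In SAP 2.5.4, supportive estimand 3, reword the handling along these lines: *treatment discontinuation for any reason other than termination of the study by the sponsor is scored as non-response at Week 16; after discontinuation because the sponsor terminated the study, data are set to missing and imputed as for the primary estimand.* State that this also applies where the estimand is used in SAP 2.6.1 and 2.6.5. Add the number of closure stops before Week 16, by arm, to the disposition table in SAP 2.3.1.

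The cost is about one sentence and one table row. There are two drawbacks. It departs slightly further from the any-reason analysis in Protocol 9.4.4, which can be met by showing the any-reason version alongside. Closure stops must also be identifiable: Protocol 5.6.2 requires the primary reason for stopping on the CRF, but the documents do not show a category for sponsor termination, so stop dates may have to be compared with the closure date. If the count proves to be zero, reporting that settles the point.

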# 2.6 Analysis of secondary objectives

Secondary objectives for the core study are to characterize the dose-response in terms of EASI and to evaluate efficacy over time.

For the extension study the secondary objectives are to evaluate the efficacy of ZPL389 when used with concomitant or intermittent TCS and/or TCI.

## 2.6.1 Dose-response for EASI50 response and EASI75 response at week 16

The dose-response analyses for EASI50 response and EASI75 response will follow similar principles as those for the IGA response. The primary estimand and the three supportive estimands will be considered in order to investigate the effect of different methods of handling data in the cases of intercurrent events.

# 2.6.2 Dose-response for percentage change from baseline in EASI at week 16

A secondary objective for core study is to characterize the dose-response relationship in terms of percentage change from baseline EASI score after 16 weeks of treatment.

The primary clinical question of interest is: What is the effect of ZPL389 versus placebo on EASI after the full 16 weeks of treatment in patients with moderate or severe atopic dermatitis, who do not use confounding therapy that may affect their AD or the assessment of it, regardless of their use of protocol-allowed concomitant medicatons?

This estimand will enable assessment of the effect of ZPL389 in the absence of confounding medication (such as rescue medication) and after the intended 16 weeks of treatment.

The main estimand is described by the following attributes:

**Population:** Adult moderate to severe atopic dermatitis patients as defined by the study inclusion and exclusion criteria who were randomized to treatment, and not mis-randomized in the IRT. This implies that analyses will be based on the full analysis set.

Endpoint: Percentage change from baseline in EASI scores at week 16.

**Treatment of interest:** the randomized treatment (ZPL389 or placebo) plus medications as allowed by the protocol but with no further treatment for patients who discontinue study treatment due an AE or lack of efficacy.

#### Handling of remaining intercurrent events:

- Use of confounding medication: set data after use of confounding medication to missing
- Treatment discontinuations for any reason: set data after discontinuation to be missing

The summary measure: difference in means between ZPL389 and placebo.

This estimand differs from that intended by the protocol in that the definition data recorded after the intercurrent events of use of confounding medication or treatment discontinuation are ignored in the analysis. The protocol had specified inclusion of all data as recorded regardless of use of confounding medication or discontinuation of treatment. This change was made to allow for an estimand for the analysis of dose-response for EASI that followed similar principles as that for the IGA response.

The following supportive estimand will also be considered to address the question of what would be the effect of ZPL389 versus placebo after treatment for up to 16 weeks and when confounding medication is allowed.

## Supportive estimand 4:

**Population:** Adult moderate to severe atopic dermatitis patients as defined by the study inclusion and exclusion criteria who were randomized to treatment, and not mis-randomized in the IRT. This implies that analyses will be based on the full analysis set.

Endpoint: Percentage change from baseline in EASI scores at week 16.

**Treatment of interest:** the randomized treatment (ZPL389 or placebo) plus medications as allowed by the protocol but with no further treatment for patients who discontinue study treatment.

#### Handling of remaining intercurrent events:

• No intercurrent events are considered.

The summary measure: difference in means between ZPL389 and placebo.

# 2.6.5 Efficacy over time up to week 16

The principles laid out for the primary estimand will be followed in calculating the summary measures for each endpoint at each time point.

The underlying clinical question in general is: What is the effect of the study treatment versus placebo on the endpoint at each week, in patients with moderate or severe atopic dermatitis, who do not use confounding therapy that may affect their AD or the assessment of it, regardless of their use of protocol-allowed concomitant medicatons, and who have received the full intended duration of treatment at that timepoint?

Other questions that may have been of interest in the case of an effective treatment, such as when is a treatment effect first seen, or how long is the treatment effect maintained for, will not be addressed.

The main secondary estimands are described by the following attributes:

**Population:** Adult moderate to severe atopic dermatitis patients as defined by the study inclusion and exclusion criteria who were randomized to treatment, and not mis-randomized in the IRT. This implies that analyses will be based on the full analysis set.

#### **Endpoints:**

IGA response at each week, where IGA response is defined as an IGA score of 0 or 1 with at least a 2 point improvement compared to baseline and no use of confounding therapy before the assessment time point.

Percentage change from baseline in EASI at each week

EASI50 response at each week, where EASI50 response is defined as a reduction from baseline of  $\geq$  50% in EASI score and no use of confounding therapy before the assessment time point.

EASI75 response at each week, where EASI75 response is defined as a reduction from baseline of  $\geq$  75% in EASI score and no use of confounding therapy before the assessment time point.

Change from baseline in peak pruritus score at each week

**Treatment of interest:** the randomized treatment (ZPL389 or placebo) plus medications as allowed by the protocol but with no further treatment for patients who discontinue study treatment due an AE or lack of efficacy.

